	Negative	A randomly selected number of patients who have not been identified by the coded search will have their records reviewed, which will show a BE diagnosis.	A randomly selected number of patients who have not been identified by the coded search will have their records reviewed and no BE diagnoses will be found.
			N/A
			Most patients not identified by the coded search will not have their records reviewed manually.

The primary endpoint will be histological confirmed BE (column “BE diagnosis” in Table 1 plus any BEs picked up by the NHS number linkage exercise) only. (The case-note review should make clear where the BE was confirmed on histology or whether it was just the impression on endoscopic that was not confirmed.) Patients with BE identified via any of the three routes (automated search plus manual confirmation, manual search, record linkage) will be considered to have BE. Patients whose records have not been searched by any of the three approaches will be considered to have missing BE status. All other patients will be considered not to have a BE diagnosis. All patients with a BE/OGD/EAC/upper GI referral should have a manual review to confirm the diagnosis; if they have not had a manual review, their BE status will be considered as (partially) missing and handled through multiple imputations (of the outcome of the missing review).

Approximate balance in the number of full case-note reviews performed at random should be ensured between the two arms for practices in the CLR group.

Important! BEs known to the study team but not identified through at least one of the three methods describes above will not count towards the primary endpoint analysis. This is most likely to apply to cases detected following a positive Cytosponge™-TFF3 stain and resulting in an endoscopy performed by a study gastroenterologist. This rule is to ensure that the same data collection methods are used in the two study arms (as trial endoscopies are not available in the usual care arm) and helps avoid any biases. However, as a sensitivity analysis, all BEs known to the study team (prior to the exit research endoscopies) will be included. . For statistics relating only to the Cytosponge™ (e.g. PPV of the TFF3 stain), all cases of BE will be included.

Assessment of secondary endpoints

To be assessed using data from the intervention arm *only* (include all BE regardless of the route of study ascertainment):

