- 1) Diagnostic accuracy of Cytosponge™ according to endoscopic findings only (focus: length of BE)
 - Positive Predictive Value (PPV) = proportion of patients with positive Cytosponge™ test result who have a confirmed BE diagnosis following endoscopy
 - PPV by length of BE detected (length of BE categories: >= C1, >= C2, >= C3)
 - Negative Predictive Value (NPV) = proportion of patients with negative Cytosponge™ test result receiving a research endoscopy after the end of the follow-up period who have a confirmed diagnosis of no BE
- 2) Performance of Cytosponge™ in detecting severity of BE, i.e. diagnostic accuracy of the test according to endoscopic and pathology findings
 - PPV of the test by severity of BE (except for score = 0)

Severity of BE for positive Cytosponge™ patients will be scored after biopsy according to the following table:

Score	BE severity
0	Pathology report not available

1	IM of oesophagus on biopsy and endoscopic findings not seen in categories below
2	C1 or C0 up to M3 + IM
3	C2 or more, C0 M4 or more + IM
4	C3 or more
5	Low grade dysplasia (LGD)
6	High grade dysplasia (HGD) or T1a cancer

- 3) Performance of Cytosponge™ in detecting IM of the gastric cardia:
 - PPV of the test for detection of IM of the gastric cardia in patients without BE, i.e. BE with IM will be excluded
- 4) Performance of Cytosponge™ in detecting BE or IM of the gastric cardia:
 - PPV of the test for detection of BE or IM of the gastric cardia, i.e. patients from endpoints 1) and 3) combined
- 5) Performance of Cytosponge™ in detecting EAC and gastric cancer:
 - PPV of the test for detecting EAC or gastric cancer
- 6) Sampling adequacy (for first test, and first and repeat test combined):

An *adequate* result is defined as: high-confidence negative (squamous and glandular cells), low-confidence positive (squamous and glandular cells with IM), or high-confidence positive (squamous and glandular cells with IM or cellular atypia).

An *inadequate* result is defined as: processing/technical failure, low-confidence negative (squamous cells only), or equivocal (squamous and glandular cells with equivocal TFF3 staining).

Sampling adequacy will be reported for the following measures for first test, and then for first and repeat test combined (i.e. not considering the result of the first test for those patients having a repeat test):

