- Cancer worry and long-term emotional or physical harm as measured by STAI-6, a short-form of the state scale of the Spielberger State-Trait Anxiety Inventory
- Perceived risk of developing EAC: overall and compared to a person of the same age

At day 7-14:

- Cancer worry and long-term emotional or physical harm as measured by STAI-6
- Perceived risk of EAC: overall and compared to a person of the same age
- Test experience as measured by visual analogue scale (0 = "Completely unacceptable", 10 = "Completely acceptable")

- Test experience as measured by the Inventory To Assess Patient Satisfaction (5-point ordinal scale with 18 items)
 - Difference in STAI-6 scores at day 7-14 and baseline
- 9) Physician/nurse acceptability of Cytosponge™: assessed through qualitative interviews (not discussed in this document).
- 10) Safety of Cytosponge™:
See Section 8.
- 11) Performance of repeat Cytosponge™ test:
- Rate of conversion to an 'adequate' result after an 'inadequate' first test result = proportion of repeat tests that have an 'adequate' result, to report with number.
 - Number/proportion of repeat tests that have an 'inadequate' result.
 - Chances of a repeat test result being TFF3 positive (high or low-confidence) after a low-confidence negative result at the first test.

The measures above will be recalculated at a second stage excluding any patients invited to a repeat test and refusing to attend.

To be assessed using data from the usual care or *both* study arms:

- 12) Number of BE diagnoses missed in current management:
- Usual care arm: research endoscopy findings
- 13) Number of undiagnosed BEs in the general population vs in the group who received Cytosponge™:
- Intervention arm: research endoscopy findings
 - Usual care arm: research endoscopy findings
- 14) Acceptability of endoscopy:
- Intervention arm: number attending Cytosponge™ appointment
 - Usual care arm: number attending research endoscopies

Proportion of participants in the usual care arm who attend their research endoscopy invitation compared to proportion of participants in the intervention arm who attend their Cytosponge™ invitation.

- 15) Number of BE diagnoses for patients with a negative Cytosponge™ result:
- Intervention arm: research endoscopy findings
- Number of false negatives of the test and false omission rate.

- 16) Quality control of endoscopic and pathology results:

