2.5.4 Variable follow-up periods

Because of delays in the implementation of the change of study design (from CLR to CLR with additional PLR group), it was decided that participants/practices could have

a follow-up longer than 12 months to compensate for participants/practices who will have a follow-up shorter than 12 months due to time constraints.

Different practices will have different follow-ups as long as the **weighted average follow-up** for the study will be greater than 12 months, as shown by the following formula:

$$\text{avg}_{\text{FU}} = \frac{\sum_{i=1}^P F_i M_i + \sum_{j=1}^Q F_j N_j}{\sum_{i=1}^P M_i + \sum_{j=1}^Q N_j} \geq 12$$

where F_i, F_j are the different lengths of follow-up (in months) for each different group, M_i are the numbers of patients with different follow-ups in the CLR group in 'equivalent size' terms, N_j are the numbers of patients with different follow-ups in the PLR group, $\sum_{i=1}^P M_i$ is the total size (in 'equivalent' terms) of the CLR group, and $\sum_{j=1}^Q N_j$ is the total size of the PLR group.

According to our current projections, all practices will have between 8 and 18 months of follow-up. The end date of follow-up will be when a site performs their local coded search; it will therefore be taken from the Coded Search case report form (CRF).

Note: in case a weighted average follow-up of 12 months or more could not be guaranteed, the power of the study would be less than 90%. The following table illustrates the potential loss in power with shorter follow-up:

Total average follow-up (months)	Factor by which to inflate sample size
9	1.24
9.5	1.18
10	1.13
10.5	1.09
11	1.06
11.5	1.03

A detailed explanation on how to calculate the factors by which to inflate the sample size is available here:

[G:\EMS\CPTU\BEST3\Section 26 STATISTICS\26.3 Power calculations\Sample size \(following Amendment 6\)\BEST3_Sample size.pdf](G:\EMS\CPTU\BEST3\Section 26 STATISTICS\26.3 Power calculations\Sample size (following Amendment 6)\BEST3_Sample size.pdf)

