3.4 Treatment assignment and treatment groups

Participants in the study were selected by an automated search in GP databases followed by a manual review of their records. All study subjects received an introductory letter to the study, allowing them 14 days to opt out of anonymised data collection. Following this, GP practices (for the CLR group) or participants (for the PLR group) were randomised to either receiving an invitation to the Cytosponge™ test or to usual care.

Non-responders of invitation to the Cytosponge™ were managed as were the patients in the usual care arm.

Participants with a positive Cytosponge™ result were invited to a **confirmatory endoscopy**. Negative Cytosponge™ patients were subsequently managed as were patients in the usual care arm.

Note: A small sample of patients in the usual care arm and negative Cytosponge™ patients were invited to a **research endoscopy** after the end of their follow-up period. The result of their research endoscopy is *not* part of the primary endpoint analysis. A handful of patients invited to the test were also invited to have a research

BEST3 SOP 008 – BEST3 Statistical Analysis Plan v1.0. [If this SAP has been printed or saved electronically, please check Sharepoint to ensure this version is the most up-to-date.](#)

endoscopy at the beginning of the roll-out of the procedure, but invitations to that group were stopped shortly thereafter, and any research endoscopy results in this group of patients will not be taken into account for any analyses.

4. Patient disposition

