The proportion of participants in the usual care arm who attend their research endoscopy invitation will be compared to the proportion of participants in the intervention arm who attend their Cytosponge™ invitation using a chi-squared test.

- 15) Number of BE diagnoses for patients with a negative Cytosponge™ result:

Number of false negatives of the test arising from research endoscopies will be used to estimate the false omission rate, where we will use as denominator the number of negative Cytosponge™ patients who attend a research endoscopy invitation. The False Omission Rate will be reported with 95% confidence interval.

- 16) Quality control of endoscopic and pathology results:

For participants swallowing the Cytosponge™ successfully:

- Number (%) of BE diagnoses missed
- Number (%) of any other malignant diagnoses missed
- Number (%) of BEs falsely detected (if any)
- A “true” PPV for BE will be calculated and presented with 95% confidence interval.

For research endoscopies, usual care arm and negative Cytosponge™ patients separately:

- Number (%) of BE diagnoses missed
- Number (%) of any other malignant diagnoses missed
- Number (%) of BEs falsely detected (if any).

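### NPV and the false omission rate count only Barrett's found at research endoscopy, against the SAP's own all-cases rule, and so probably understate the false omission rate modestly

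*SAP*

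**What the plan says.** Item numbers are those of SAP Sections 2.3 and 7.1.2.

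- **NPV (Section 2.3, item 1)** is the "proportion of patients with negative Cytosponge™ test result receiving a research endoscopy after the end of the follow-up period who have a confirmed" absence of BE.
- **False omission rate (Section 7.1.2, item 15).** The numerator is fixed by "Number of false negatives of the test arising from research endoscopies will be used to estimate the false omission rate", and the denominator by "we will use as denominator the number of negative Cytosponge™ patients who attend a research endoscopy invitation". In Section 2.3 the same item gives research endoscopy findings as its only data source and promises the "Number of false negatives of the test and false omission rate".
- **Care between test and research endoscopy.** Section 3.4 says "Negative Cytosponge™ patients were subsequently managed as were patients in the usual care arm". Section 2.5.4 projects that "all practices will have between 8 and 18 months of follow-up".
- **General rule (Section 2.3, end of the primary endpoint text):** "For statistics relating only to the Cytosponge™ (e.g. PPV of the TFF3 stain), all cases of BE will be included". The heading over the intervention-arm-only endpoints adds that BE counts whatever the route of ascertainment. That heading covers item 1 but not item 15, which is listed under usual care or both arms.
- **Item 12 (Section 7.1.2)** estimates total BE in test-negatives as T2. It adds B12 − B14 − B15 − B16 (cases found outside research endoscopy) to B11 (cases found at research endoscopy) and to a projected number still missed.

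**The concern.** A test-negative patient with BE who is referred clinically and diagnosed during follow-up is a known false negative. Items 1 and 15 have no place for that patient: neither numerator nor denominator draws on anything but research endoscopies done after follow-up ends. The title of item 15 covers BE diagnoses in test-negative patients generally, so its definition is narrower than its title.

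Two things are at stake. First, an analyst cannot follow both the all-cases rule and the specific definitions, so the reported NPV depends on which is chosen. Second, followed as written, the figures probably describe BE still undiagnosed after 8 to 18 months of usual care. That is not what a negative result meant on the day it was given.

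**Working it through.** **Inputs (SAP Section 2.5.2 unless noted).** BE prevalence 0.04; endoscopy referral in usual care 0.10; BE among those referred 0.06; endoscopy sensitivity 1. Test sensitivity s is 0.85, or 0.80 in item 12. Uptake is 0.27 planned and 0.24 observed (Section 2.5.3). Participants number 13,234, so 6,617 per arm if split 1:1. Specificity is not given; I assume 0.95 to 1.00.

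**Reproducing the SAP's figures.** Intervention arm: 0.27 × [0.04 × 0.85 + 0.15 × 0.10 × 0.06] + 0.73 × 0.10 × 0.06 = 0.27 × 0.0349 + 0.00438 = 0.013803, the stated 1.38%. Usual care: 0.10 × 0.06 = 0.6%. Two proportions at 90% power and two-sided 5% give 3,382 per arm (6,764) with the unrounded rate. The term 0.15 × 0.10 × 0.06 is the group at issue: false negatives later diagnosed in usual care.

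**Share left out at 12 months, per person tested.**
- False negatives: (1 − s) × 0.04 = 0.0060 (s = 0.85) or 0.0080 (s = 0.80).
- Diagnosed in usual care: (1 − s) × 0.006 = 0.0009 or 0.0012.
- Share: 0.006/0.04 = 15%, whatever the sensitivity.

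**In cases.** Tested: 6,617 × 0.24 ≈ 1,588. At s = 0.85, 1,588 × 0.0060 ≈ 9.5 false negatives, of which 1,588 × 0.0009 ≈ 1.4 are diagnosed in follow-up. At s = 0.80, about 12.7 and 1.9.

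**False omission rate (FOR).** Negatives per person tested = false negatives + 0.96 × specificity. All cases: FOR = false negatives / negatives. As planned, with diagnosed cases absent: FOR = (false negatives − diagnosed) / (negatives − diagnosed).

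| s | Specificity (assumed) | FOR, all cases | FOR, as planned |
|---|---|---|---|
| 0.85 | 0.95 | 0.0060/0.9180 = 0.65% | 0.0051/0.9171 = 0.56% |
| 0.85 | 1.00 | 0.0060/0.9660 = 0.62% | 0.0051/0.9651 = 0.53% |
| 0.80 | 0.95 | 0.0080/0.9200 = 0.87% | 0.0068/0.9188 = 0.74% |
| 0.80 | 1.00 | 0.0080/0.9680 = 0.83% | 0.0068/0.9668 = 0.70% |

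The relative understatement is about 15% in every row, and NPV is about 0.1 percentage point too high. Scaling diagnoses by months/12, the understatement is about 10% at 8 months and 22% at 18 months.

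**Sampling error.** The SAP gives no number of research endoscopies, only that the sample is small. With no BE found in an assumed 50, 100 or 150, the exact 95% upper limit is 7.1%, 3.6% or 2.4%. With 1 BE in an assumed 200 the interval is 0.01% to 2.8%. All are far wider than a shift of 0.1 point.

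**The case against.** **The direction rests on an unstated rule.** No section says that patients already diagnosed with BE are kept out of the research endoscopies. This stands as a caveat. The SAP's own formulae point that way, however: T2 would count such patients twice, and item 13 treats BE found at research endoscopy as undiagnosed. BE arising after the test, and self-selection of attenders, could act in the opposite direction and cannot be quantified from the document.

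**The contradiction may be narrower than it looks.** The any-route heading does not reach item 15. The all-cases sentence closes a paragraph on cases missed by the three systematic searches, and its example is PPV. Restricting to patients who had endoscopy also gives everyone counted the same reference test. That is a fair reading, but NPV and the false omission rate are plainly statistics on the test alone, and Section 7.1.2 says secondary endpoints using BE diagnoses rely on the actual trial data. The conflict is direct for item 1 and real, if less direct, for item 15.

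**A reader might infer that the trial could report no false negatives and an NPV of 100% while its database already holds diagnosed ones.** With an assumed 50 to 150 research endoscopies, the chance of finding no BE is roughly 33–77%. But that follows from a small sample, not from this definition. Item 15 requires a confidence interval, so a zero would not stand alone. Nor is a clinically diagnosed false negative assured: with means of 1.4 and 1.9, the Poisson chance of none is about 24% and 15%.

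**Further detail is deferred.** Section 7.1.2 promises a supplementary SAP, which is not at hand. It may settle the matter, but it does not remove the conflict in this document.

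**Conclusion.** The point holds as an inconsistency of definition with a modest probable bias. As written, items 1 and 15 leave out BE diagnosed clinically during follow-up in test-negatives, while the general rule in Section 2.3 and T2 in item 12 include it.

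The size rests on three assumptions: patients already diagnosed are not counted at research endoscopy; usual care finds missed BE at the rate implied by the sample size inputs; and specificity is 95–100%. The shift is not large, and it cannot be called certain to favour the test. A reader might also take it as a bias in the estimated sensitivity, but the false omission rate is not one minus sensitivity, and item 12 already counts these cases when it estimates missed BE.

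These are secondary, descriptive measures, and the primary endpoint is untouched. Severity is minor and confidence moderate.

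**What to change.** 1. Reconcile the all-cases rule in Section 2.3 with items 1 and 15 in Sections 2.3 and 7.1.2. State whether patients with a BE diagnosis during follow-up could be invited to, or counted at, research endoscopy.
2. In items 1 and 15, report two components side by side: b_clin, the BE diagnosed clinically during follow-up among all N_neg test-negatives; and b_res/n_res, the yield of research endoscopy in negatives without a prior BE diagnosis.
3. Estimate FOR = [b_clin + (N_neg − b_clin) × b_res/n_res] / N_neg, and NPV = 1 − FOR. Do not simply add b_clin to the numerator over n_res, because that would overstate the rate.
4. Use an interval that stays valid when b_res = 0. With p = b_clin/N_neg and r = b_res/n_res, FOR = p + (1 − p) × r, which rises in both. Insert the 97.5% Clopper-Pearson limits of p and r to obtain conservative 95% coverage. A bootstrap or delta-method interval should not be used, since its research part has zero variance when b_res = 0. Illustration with assumed counts b_clin = 1, N_neg = 1,458 (1,588 × 0.918), b_res = 0 and n_res = 100: the delta-method upper limit is about 0.20%, below the 0.65% expected on the SAP's inputs. The proposed limit is 0.0044 + 0.9956 × 0.0429 ≈ 4.7%.
5. Keep the research-endoscopy-only figure with its exact interval as a supporting result, labelled residual undiagnosed BE after follow-up.

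**Cost.** Some SAP wording and a little code; the counts are already needed for item 12. The interval is wider (in the illustration 4.7% against 3.6% for the research-only upper limit), and the NPV is likely to be slightly less favourable.

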7.1.3 Analysis of further subgroups

Because of the nature of the data, we only have individual-level information available for Cytosponge™ patients. Exploratory analyses may be performed by subgroup created using data gathered during the Cytosponge™ appointment, such as age group, gender, BMI, smoking history, etc.

7.2 Covariates

No covariates will be introduced in the primary endpoint analysis because of the type of analysis and the structure of the data available (see Section 7.1.1.2). It should be noted, however, that the primary endpoint analysis will be performed by period (up to 4 months vs from 4 to 18 months).

7.3 Methods for handling missed data and outliers

Any outliers found in the data will be checked with the study sites when possible. Otherwise, they will be substituted by empty fields.

7.3.1 Handling of dropouts

All study subjects received a letter before their follow-up began to inform them about the use of their data within the Trial and to give them the option of opting out of it before 14 days. However, in a handful of cases, participants withdrew consent to the study after the 14-day period (or the practice alerted the trials team late about the objection) and their records were consequently deleted from the Trial database. File notes were filled in for each one of these withdrawals.

As intervention subjects received further letters inviting them to the Cytosponge™ test, it is more likely that they will have withdrawn of the Trial after the 14-day opt-out period in a higher number than usual care patients. For a similar argument, intervention practices in the CLR group, who were more involved in the trial, were more likely to report to the trials team any late opt-outs than usual care practices.

It should also be noted that, in the PLR group, a handful of patients also opted out after being randomised.

Number of dropouts will be reported on, but they will be excluded from any endpoint analysis. However, because of the aggregated (i.e. site-level) nature of the data on age groups and medications, we will not be able to exclude these patients from any summary statistics on these baseline characteristics. A further sensitivity analysis will see dropouts not excluded and treated as participants without BE.

7.3.2 Handling of missing data in active subjects

We do not expect to see any missing data for any primary or secondary endpoints, except for those outcomes linked to patient acceptability questionnaires, for any BEST3 SOP 008 – BEST3 Statistical Analysis Plan v1.0. [If this SAP has been printed or saved electronically, please check Sharepoint to ensure this version is the most up-to-date.](#)

outcomes measured in patients who died or moved away during the trial, and for any sites not performing any manual case-note reviews of their records at the end of follow-up.

As we expect very low percentages of missing data, when dealing with missing values for an endpoint analysis, we will exclude individual records accordingly..

8. Safety analysis

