3.2 Study populations

3.2.1 Intention-to-treat population

The intention-to-treat (ITT) population will include all participants enrolled into the study. The following participants will be *included* in the ITT analysis:

- Deceased patients:
BE status at death will be used as their BE status at the end of the trial.
- Study subjects that moved away from a practice:
We are unlikely to know how long such patients were followed because we only receive aggregate data regarding most patients. For this reason, we will treat them as if they were followed for the same duration as other patients in that practice unless we know when they moved, in which case their follow-up will be treated as censored at that time.
- Participants lost to follow-up due to local information governance restrictions:
If we have no follow-up on all patients in a particular practice, that practice will effectively be excluded. The fact that this has happened will be noted. Individuals with a Cytosponge™ test will still be included in the intervention-arm only results assuming that BE found as a result of a positive Cytosponge™ will have been recorded. If a patient withdraws consent for their data to be used for research purposes ('Type 2' objection), they will be excluded.

As detailed data are only available for consented patients in the intervention arm, for all patients we assume a follow-up equal to the follow-up of their practice, with the exception of any known participants invited to a research endoscopy before the end of their follow-up period. However, it should be noted that IDs of participants with a BE/OGD/EAC/upper GI referral will be collected for both arms and available for the statistical analysis.

Subjects who opted out (Type 2 objection to their data being used, or explicitly writing to the study team asking for their data to be removed from the database) *after* being entered into the study (i.e. more than 14 days after receiving the trial introductory letter) will be *excluded* from the ITT analysis and any further analyses. The numbers of such patients in each arm will be reported.

Further exploratory epidemiological analyses to study the risk of BE according to baseline/demographics data may be detailed in a separate SAP for epidemiological analyses.

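### SAP 2.3 imputes, but 7.3.2 excludes, coded-search-flagged patients who had no manual review; the primary endpoint needs one rule

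*SAP*

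**What the plan says.** Section 2.3 of the SAP sorts patients by how their records were searched. A patient with a coded BE, endoscopy, adenocarcinoma or upper GI referral should have a manual review. For such patients, "if they have not had a manual review, their BE status will be considered as (partially) missing and handled through multiple imputations". Patients whose records were searched by none of the three routes have missing status, and no imputation is stated for them. For the rest, "All other patients will be considered not to have a BE diagnosis", so an unflagged patient at a searched site stays in the denominator as a non-case.

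Section 7.3.2 opens with "We do not expect to see any missing data for any primary or secondary endpoints". Its exceptions are questionnaire outcomes, patients who died or moved away, and a gap expected "for any sites not performing any manual case-note reviews of their records at the end of follow-up". Because little missing data is expected, the rule for a missing value in any endpoint analysis is: "we will exclude individual records accordingly". There is no cross-reference to 2.3 and no carve-out for the primary endpoint.

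Section 3.2.1 keeps deceased patients and movers in the intention-to-treat population. For the deceased, "BE status at death will be used as their BE status at the end of the trial". Movers are given their practice's follow-up, or are censored at the move date if it is known.

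**The concern.** Both sections address BE status that is missing because no manual review was done, and they prescribe different handling. Under 2.3, at a site that ran its coded search but did no reviews, the unflagged patients already count as no BE. The patients with missing status there are the flagged ones, who are also the patients most likely to have BE. Applying 7.3.2 would delete them and keep the unflagged person-time, so without linkage such a site would contribute follow-up and no cases. Missingness of this kind depends on the probable outcome.

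A low percentage of missing records therefore gives little reassurance. What matters is the share of flagged patients who were not reviewed. Section 7 also has two statisticians analyse the primary endpoint independently and reach consensus if they differ. Each could follow a different section and still comply, and the choice of rule would then be made with results in view.

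**Working it through.** **Plan's own figure.** Section 2.5.2 takes 10% referred to endoscopy in usual care, BE in 6% of those referred, BE prevalence 4%, test sensitivity 85% and uptake 27%.

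- Usual care: 0.10 × 0.06 = 0.6%.
- Intervention: 0.27 × [0.04 × 0.85 + 0.15 × 0.10 × 0.06] + 0.73 × 0.10 × 0.06 = 1.3803%.
- Two proportions, pooled variance under the null, two-sided 5%, 90% power: 3382 per arm, 6764 in total, as the SAP states. (The rounded 1.38% gives 6768.)
- Planning rate ratio: 1.38 / 0.6 = 2.30.

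**Assumptions for the illustration.** The SAP gives no non-review fraction, so f below is hypothetical.

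- The flagged share q is 10% in both arms, borrowing the SAP's referral figure. Using 12% in the intervention arm changes power by less than 1 percentage point.
- All BE lies among flagged patients, and unreviewed flagged patients have the same BE proportion as reviewed ones.
- NHS linkage recovers none of them.
- Proportions stand in for rates, as in the SAP's sample size section.

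**Formula.** If a fraction f of flagged patients is unreviewed and excluded, a fraction f of the cases goes but only f × q of the denominator:

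observed rate = true rate × (1 − f) / (1 − 0.1f).

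**Equal f in both arms**

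| f | Records missing | BE cases lost | Rate multiplier | Usual care | Intervention | Rate ratio | Power |
|---|---|---|---|---|---|---|---|
| 0% | 0% | 0% | 1 | 0.60% | 1.38% | 2.30 | 90.0% |
| 5% | 0.5% | 5% | 0.955 | 0.57% | 1.32% | 2.30 | 88.5% |
| 10% | 1% | 10% | 0.909 | 0.55% | 1.25% | 2.30 | 86.7% |
| 20% | 2% | 20% | 0.816 | 0.49% | 1.13% | 2.30 | 82.5% |
| 30% | 3% | 30% | 0.722 | 0.43% | 1.00% | 2.30 | 77.3% |

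At f = 20% the multiplier is 0.80 / 0.98 = 0.816, a fall of about 18%, and the sample per arm is 3382 × 0.98 = 3314. The multiplier cancels in the ratio, so equal non-review costs power and lowers absolute rates but leaves the rate ratio alone.

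**Unequal f, for sensitivity only.** If the 20% fell wholly in usual care, the ratio would be 2.30 / 0.816 = 2.82. If it fell wholly in the intervention arm, it would be 2.30 × 0.816 = 1.88.

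**The case against.** Four things can be said for the plan.

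1. **Review of flagged patients is the planned procedure.** Section 2.3 assigns manual review to everyone found by the coded search, and site capacity limits only the additional reviews. Section 3.2.2 says late practices may skip reviews other than those of flagged patients. The real f may be near zero. This stands and limits the size, but 2.3 and 7.3.2 both provide for reviews not being done.
2. **The specific rule could be taken to override the general one.** Section 2.3 names the patient group and the method. That reading is natural, but the SAP does not say so, and 7.3.2 itself names sites without reviews. The imputation in 7.1.1.3 does not settle it either: it is a sensitivity analysis of what would have been found had all three search methods been used for everyone.
3. **Exclusion does not only hit flagged patients.** It also reaches records searched by no route, where 2.3 prescribes no imputation and there is no conflict. At linked sites, a BE found by linkage counts, so that patient is not missing.
4. **The death and mover wording is loose more than contradictory.** Section 3.2.1 supplies status at death, so nothing is missing for those patients. For movers it sets follow-up time.

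A reader might infer a biased treatment effect, especially since 7.3.1 describes intervention practices in the cluster-randomised group as more engaged with the trial. The SAP does not support that inference. The remark concerns reporting of late opt-outs, not completion of case-note reviews. In the patient-level group each practice serves both arms, so a site without reviews affects both.

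**Conclusion.** The contradiction is real and concerns who counts as a case in the primary analysis. Sections 2.3 and 7.3.2 give opposite instructions for flagged patients without a manual review, and the exclusion rule is the harmful one because it drops probable cases while keeping unflagged patients as no BE.

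The demonstrable consequences are lower detection rates and lost power. On the assumptions set out above, 20% non-review in both arms lowers the BE rate by about 18% and brings power from 90% to about 82.5%, with the rate ratio unchanged. These figures illustrate the mechanism; they do not forecast the trial, because the non-review fraction is not in the SAP and may be small. Bias in the rate ratio requires non-review to differ by arm, which is possible but not shown.

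**What to change.** Amend 7.3.2 so that, for the primary endpoint:

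- The exclusion rule does not apply to flagged-but-unreviewed patients. They are multiply imputed as in 2.3, with trial arm in the imputation model.
- Unflagged patients at searched sites count as no BE, as 2.3 already says.
- Deaths and movers follow 3.2.1.
- Exclusion stays for records searched by none of the three routes. Deleting the rule outright would leave those individuals without any rule, since 3.2.1 deals only with whole practices lacking follow-up.

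Outside the primary endpoint, 7.3.2 can stand. Report a complete-case analysis of the primary endpoint as a sensitivity analysis.

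The cost is mostly wording, because imputation is already planned. The one real addition is a short imputation model, which 2.3 does not give and which must be specified before data lock.
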